#### AE Reporting

Expected AEs will be reported to the institutional IRB and reviewed at the time of the annual review. Any SAEs or multiple occurrences of an AE determined to be an unanticipated problem will be reported to Johns Hopkins Institutional Review Board, the Johns Hopkins Cancer Center Clinical Research Committee, and the Johns Hopkins Institutional Biosafety Committee. SAE’s will be reported to all regulatory agencies within 7 working days. Unanticipated or unexpected AE is defined as any AE not listed in available sources including the labeling, the Investigator’s Brochure, or this protocol.

### **11.8 Definition of Dose-Limiting Toxicity**

A dose-limiting toxicity is defined as any grade 3 toxicity in any organ system, or grade 2 or higher allergic reaction/hypersensitivity reaction (allergy/immunology), as delineated in CTCv4.0.

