**Toxicities and Adverse events**

**Table 5: Solicited General Signs and Symptoms**

Adverse Event	Short Name	Grade 1	Grade 2	Grade 3	Grade 4	Grade 5
Allergic reaction/hypersensitivity (including drug fever)	Allergic reaction	Transient flushing or rash; drug fever <38°C (<100.4°F)	Rash; flushing; urticaria; dyspnea; drug fever ≥38°C (≥100.4°F)	Symptomatic bronchospasm, with or without urticaria; parenteral mediation(s) indicated; allergy-related edema/angioedema; hypotension	Anaphylaxis	Death
Fever (in the absence of neutropenia, where neutropenia is defined as ANC <1.0 x 10  /L)	Fever	38.0-39.0°C (100.4-102.2°F)	>39.0-40.0°C (102.3-104.0°F)	>40.0°C (104.0°F) ≤24 hours	>40.0°C (104.0°F) >24 hours	Death
Cytokine release syndrome/acute infusion reaction	Cytokine release syndrome	Mild reaction; infusion interruption not indicated; intervention not indicated	Requires therapy or infusion interruption but responds promptly to symptomatic treatment (e.g., antihistamines, NSAIDs, narcotics, IV fluids); prophylactic medications indicated for ≤24hrs	Prolonged (i.e., not rapidly responsive to symptomatic medication and/or brief interruption of infusion); recurrence of symptoms following initial improvement; hospitalization indicated for other clinical sequelae (e.g. renal impairment, pulmonary infiltrates)	Life-threatening; pressor or ventilatory support indicated	Death

Nervous system disorder	Head aches	Mild pain	Moderate pain, limiting instrumental ADL	Severe pain, limiting self care, ADL	—	-
Nervous system disorder	Dizziness	Mild unsteadiness or sensation of movement	Moderate unsteadiness or sensation of movement, limiting instrumental ADL	Severe unsteadiness or sensation of movement; limiting self care ADL	—	-
Ear and labyrinth disorder	Tinnitus	Mild symptom intervention not indicated	Moderate symptoms, limiting instrumental ADL	Severe symptoms, limiting self care ADL	-	-

Patients will be monitored throughout the study for both known potential risks and for unexpected risks. During office visits, patients will be monitored specifically for any signs of:

- Symptoms of itching, burning, pain, warmth, or tenesmus
- Signs of skin breakdown including erythema, blistering, desquamation, ulceration or bleeding
- Neurologic symptoms
- Unexpected adverse events

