All unexpected and related SAEs will be reported immediately to [name], who will remove any at-risk patient from the study. Any subject who shows evidence of a drug-related SAE (grade III or IV) will be removed from the study and the SAE will be reported to the FDA and the JHMIRB within 7 working days of finding out.

Risks to privacy of individuals, confidentiality of data: There is a potential risk of loss of confidentiality. To ensure that all information and specimens collection remain

confidential and anonymous, all study data will be de-identified. Only the research team will have access to study participant private data. All study specimens are de-identified and cannot be linked to the subjects. Specimens will be barcoded before storage so that patient identifiers will not be available to the laboratories performing the assays proposed in this application.

To ensure that all study data remains confidential, all study data will be maintained on a password-protected database. Patient identifying information will not be associated with the study research data. Only the research investigators will be able to access a list connecting patient identifiers with the study ID, and this can only be provided upon special request from the study database managers.

The rate at which invasive cancer develops from CIN is slow and can take years and perhaps decades [49]. The fifteen-week treatment study window precedes the standard LEEP or cone excisional biopsy procedure given to the targeted study population, and therefore will not extend the normal time clinicians allow between disease detection and therapy and as such, participation in this study will not affect optimal patient treatment.

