#### **11.7 Recording and Follow-up of Adverse Events**

The severity of each adverse event must be assessed using the NCI Common Terminology Criteria for Adverse Events, v4.0 (CTCAE 4.0).

All adverse events that occur from the time of study drug administration through 30 days after the final treatment will be recorded. Duration, severity, treatments administered and outcome for each adverse event will be recorded on the CRF for the following visit. Drug related adverse events will be followed until resolved, until no further improvement is expected, until a non-study antitumor therapy is initiated, or for 30 days after last study treatment, whichever comes first (with the exception of neuropathy, which must be followed until resolution to  $\leq$  grade 1 or until stable for 60 days).

Adverse events beginning 30 days after the last treatment that the investigator considers to be related to study treatment will be reported to the appropriate contact person at any time such events occur.

Conditions that were present at the study start and that worsen during the study should be reported as beginning on the date the event worsened, not the date it began pre-study. Event text may include the word “worsened” or “exacerbated.”

Conditions which were recorded as “intermittent” at the study start which occur during the study must be reported if they are more frequent or of greater severity.

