### **11.9 Early stopping rules**

Because this is a pilot study evaluating tolerability of a new intra-vaginal treatment, the stopping rule for safety is the presence of Grade 3 toxicity in any organ system, or grade 2 or higher allergic/hypersensitivity reaction as delineated in CTCAEv4.0. In the event of two identical unexpected related treatment-related Grade 3 toxicities, accrual will be suspended pending further review.

Subjects who become pregnant during study will be required to discontinue drug. Although not considered an adverse event, pregnancy will be reported in the same way. Whenever possible, a pregnancy should be followed to term, and the status of mother and child reported. The Pregnancy Notification form will be sent by sites to the study sponsor ([name]) within 48 hours of discovery. Whenever possible, the Follow-up Pregnancy Outcome Form will be filled after delivery.

Finally, if there is evidence of disease progression at the interval visit regardless whether the progression may or may not be associated with Artesunate, patients will undergo resection at that point.

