## **12.0 STATISTICAL CONSIDERATIONS**

### **12.1 Study Design/Endpoints/Accrual**

The primary statistical outcome of the trial is safety. The treatment groups will be filled sequentially in a non-blinded manner. Study dropouts will be replaced.

The dose escalation algorithm is described as follows (see Table 4 for dose levels to be tested):

1. A run-in cohort of three patients will be treated with one 5-day cycle of 50mg vaginal suppositories. If no patient has a DLT observed by the cervix check visit after the last suppository, the trial will proceed to the next level.
2. A cohort of 9 patients will be enrolled and treated with one 5-day cycle of 200mg vaginal suppositories. If no patient has a DLT observed by the cervix check after the last suppository, the dose level will be considered tolerable and the trial will proceed to the next level.
3. If exactly one of the 9 patients has a DLT by Week 1-2 after the last suppository, three more patients will be enrolled and treated at the current dose level. If none of the three patients has a DLT by the cervix check after the last suppository, the current dose level will be considered safe and dose will be escalated.
4. If two or more of the 9 or 12 patients have a DLT observed by Week 1-2 cervix check, dose escalation will be stopped. The current dose level will be considered unsafe.
5. A cohort of 9 patients will be enrolled and treated with 2 cycles of 200 mg vaginal suppositories, at 2-week intervals. If no patient has a DLT observed in Cohorts II and III, then the dose level will be considered safe, and the dose will be escalated.
6. A cohort of 9 patients will be enrolled and treated with 3 cycles of 200 mg vaginal suppositories, at 2-week intervals. If no patient has a DLT observed by the cervix check after the last suppository, then the dose level will be considered safe.

With the dose escalation algorithm, there will be less than 9% probability to escalate to the next higher dose level if the DLT rate for the current dose level is 30%.

The maximum sample size for dose escalation is 39. Based on our experience in investigator-initiated therapeutic trials in this patient population at this institution, our anticipated accrual rate is 20-25 patients per year.

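### The DLT definition (11.8) and safety stopping rule (11.9) name only grade 3 for non-allergic toxicity, so as written a non-allergic grade 4 or 5 event is neither a DLT nor a stopping event

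*Combined protocol and SAP*

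**What the plan says.** **DLT definition (Section 11.8).** "A dose-limiting toxicity is defined as any grade 3 toxicity in any organ system, or grade 2 or higher allergic reaction/hypersensitivity reaction". The qualifier that extends the rule to higher grades is attached to the allergic limb only.

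**Stopping rule (Section 11.9).** The text has the same structure: "the stopping rule for safety is the presence of Grade 3 toxicity in any organ system, or grade 2 or higher allergic/hypersensitivity reaction". The next sentence also names a single grade: "In the event of two identical unexpected related treatment-related Grade 3 toxicities, accrual will be suspended pending further review".

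**Individual removal (Section 11.5).** "Any subject who shows evidence of a drug-related SAE (grade III or IV) will be removed from the study". Grade IV is named here; grade V is not.

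**Grading scale.** Section 11.7 requires CTCAE version 4.0. Table 5 has columns for grades 4 and 5. It fills them for fever and for cytokine release syndrome, each in a row separate from allergic reactions. Grade 4 fever is ">40.0°C (104.0°F) >24 hours".

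**Use of the count (Section 12.1).** At the first 200 mg level, "If no patient has a DLT observed by the cervix check after the last suppository, the dose level will be considered tolerable". One DLT in nine adds three patients, and two or more DLTs in nine or twelve stop escalation. Levels II to IV that are judged safe are then candidates for a 12-patient expansion.

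**The concern.** Safety is the primary statistical outcome, and from Cohort II on every decision step in Section 12.1 is a count of DLTs. If the definition omits the most severe non-allergic grades, the count can fall as severity rises. The drafters wrote an open-ended threshold for allergic reactions in the same sentence, so a reader cannot simply assume that the other limb is open-ended too. Section 11.5 shows that they could also name grade IV explicitly when they meant to.

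At stake is whether a level with a very severe event can be called tolerable, passed to a more intensive schedule, or selected for expansion without that event having counted.

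**Working it through.** **Step 1: the sections side by side, for a non-allergic event.**

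| Section | Acts on | Grade 3 | Grade 4 | Grade 5 |
|---|---|---|---|---|
| 11.8 DLT | cohort count | named | not named | not named |
| 11.9 stopping rule | trial | named | not named | not named |
| 11.9 accrual suspension (two identical, unexpected, related) | accrual | named | not named | not named |
| 11.5 removal (drug-related SAE) | one subject | named | named | not named |

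No other section says that non-allergic grades 4 and 5 count as DLTs.

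**Step 2: a worked case from Table 5.** A fever above 40.0°C lasting up to 24 hours is grade 3 and literally a DLT. The same fever lasting longer is grade 4 and literally not one. Headache, dizziness and tinnitus have no grade 4 or 5 entry in Table 5. Among the solicited events listed there, the gap therefore affects fever and cytokine release syndrome. It also affects any other non-allergic event that CTCAE grades 4 or 5.

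**Step 3: effect on one cohort.** Nine patients are treated at 200 mg. One has a non-allergic grade 4 or 5 event and nobody else has a qualifying event. The literal count is 0 of 9. Section 12.1 treats the level as tolerable and moves on, and neither sentence of 11.9 quoted above is triggered. If the event were counted, the tally would be 1 of 9.

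**Step 4: the plan's own figures.** Section 12.1 states a probability below 9% of escalating when the DLT rate is 30%.
- Sequential rule as written, pass on 0 of 9, or on 1 of 9 followed by 0 of 3: (1−p)^9 + 9p(1−p)^8 × (1−p)^3. At p = 0.30 this is 0.0404 + 0.0534 = 9.37%.
- At most 1 DLT in a fixed 12: 0.7^12 + 12 × 0.3 × 0.7^11 = 0.0138 + 0.0712 = 8.50%.

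The second matches the stated bound. The first exceeds it by 0.37 percentage points, which is a separate and small matter. The stated maximum of 39 is 3 + 3 × 12.

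**Step 5: illustration of size.** Let s be the share of affected patients whose only qualifying event is a non-allergic grade 4 or 5. The documents do not give s, so it is an assumption. With a total rate of 30%, the counted rate is 0.30(1−s). The third column applies 12.1 alone. The last column allows a level to pass only with no counted event in nine, (1−p)^9, which is what follows if 11.9 is read as stopping the trial at the first counted event.

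| s | counted rate | pass, 12.1 alone | pass, 0 of 9 only |
|---|---|---|---|
| 0 | 0.300 | 9.4% | 4.0% |
| 5% | 0.285 | 11.3% | 4.9% |
| 10% | 0.270 | 13.5% | 5.9% |
| 20% | 0.240 | 19.0% | 8.5% |
| 30% | 0.210 | 26.1% | 12.0% |

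On either reading, a share of 30% raises the pass probability nearly threefold.

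**The case against.** The strongest reply is that a DLT rule naming grade 3 is ordinarily read as a minimum, that the omission is probably a drafting slip, and that no investigator would ignore a grade 4 or 5 event. Such events would also not go unreviewed. Section 11.5 requires immediate reporting of unexpected related SAEs, the AE reporting text in 11.7 sends SAEs to the regulatory agencies within 7 working days, and Section 14 places monitoring with a Safety Monitoring Committee. Section 5 expects no dose-limiting toxicities. All of this is fair and limits the practical risk. It does not supply the missing definition: none of these provisions says what enters the 12.1 count.

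Four stronger inferences are tempting, and the documents do not support them.
- *That 11.5 contradicts 11.8 and 11.9 for grades 4 and 5.* Section 11.5 acts on one subject, and the others act on the cohort or trial, so both can be followed at once. A subject can be removed for a non-allergic grade IV event that is not counted, which is a mismatch of thresholds. For grade 5 there is no mismatch, because 11.5 does not name it either.
- *That one uncounted event turns two of nine, which stops, into one of nine, which adds three patients.* The remaining counted event would itself meet the stopping rule in 11.9. The extra three patients do not follow until the relation between 11.9 and 12.1 is settled.
- *That the DLT count is the only gate throughout.* Escalation after Cohort I has separate conditions in Sections 3.2, 5.0 and 11.2, which turn on any adverse event, side effect, irritation or toxicity.
- *That replacing dropouts erases their events.* The replacement text concerns cohort numbers and is silent on whether an event in a replaced subject still counts.

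**Conclusion.** The point stands as a wording omission in a rule that drives decisions. As written, non-allergic grade 4 and 5 events are outside both the DLT definition and the stopping rule, although the trial's own scale includes them. The gap matters mainly for Cohorts II to IV, which are all the 200 mg cohorts, and it is clearest when such an event is the only severe one in a cohort of nine.

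The textual finding needs no assumption beyond a literal reading. The percentages depend on an assumed total rate of 30%, taken from the plan's own operating characteristic, and on an assumed uncounted share. They show how sensitive the rule is to the omission. They do not estimate harm in this trial.

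**What to change.** Reconcile Sections 11.5, 11.8, 11.9 and 12.1 so that one explicit set of grades governs both the DLT count and the stopping rule, with a plain statement of how grades 4 and 5 are treated. Aligning 11.8 and 11.9 only with the grades that 11.5 names would still leave grade 5 unaddressed. In the same amendment, state how the 11.9 stopping rule relates to the branch in 12.1 that adds three patients after one DLT. Which grades belong in each rule is for the sponsor and investigators to decide.

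The cost is a wording amendment with the usual IRB approval. Settling the treatment of grades 4 and 5 changes neither the sample size nor any study procedure.

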### **11.9 Early stopping rules**

Because this is a pilot study evaluating tolerability of a new intra-vaginal treatment, the stopping rule for safety is the presence of Grade 3 toxicity in any organ system, or grade 2 or higher allergic/hypersensitivity reaction as delineated in CTCAEv4.0. In the event of two identical unexpected related treatment-related Grade 3 toxicities, accrual will be suspended pending further review.

Subjects who become pregnant during study will be required to discontinue drug. Although not considered an adverse event, pregnancy will be reported in the same way. Whenever possible, a pregnancy should be followed to term, and the status of mother and child reported. The Pregnancy Notification form will be sent by sites to the study sponsor ([name]) within 48 hours of discovery. Whenever possible, the Follow-up Pregnancy Outcome Form will be filled after delivery.

Finally, if there is evidence of disease progression at the interval visit regardless whether the progression may or may not be associated with Artesunate, patients will undergo resection at that point.

## **12.0 STATISTICAL CONSIDERATIONS**

### **12.1 Study Design/Endpoints/Accrual**

The primary statistical outcome of the trial is safety. The treatment groups will be filled sequentially in a non-blinded manner. Study dropouts will be replaced.

The dose escalation algorithm is described as follows (see Table 4 for dose levels to be tested):

1. A run-in cohort of three patients will be treated with one 5-day cycle of 50mg vaginal suppositories. If no patient has a DLT observed by the cervix check visit after the last suppository, the trial will proceed to the next level.
2. A cohort of 9 patients will be enrolled and treated with one 5-day cycle of 200mg vaginal suppositories. If no patient has a DLT observed by the cervix check after the last suppository, the dose level will be considered tolerable and the trial will proceed to the next level.
3. If exactly one of the 9 patients has a DLT by Week 1-2 after the last suppository, three more patients will be enrolled and treated at the current dose level. If none of the three patients has a DLT by the cervix check after the last suppository, the current dose level will be considered safe and dose will be escalated.
4. If two or more of the 9 or 12 patients have a DLT observed by Week 1-2 cervix check, dose escalation will be stopped. The current dose level will be considered unsafe.
5. A cohort of 9 patients will be enrolled and treated with 2 cycles of 200 mg vaginal suppositories, at 2-week intervals. If no patient has a DLT observed in Cohorts II and III, then the dose level will be considered safe, and the dose will be escalated.
6. A cohort of 9 patients will be enrolled and treated with 3 cycles of 200 mg vaginal suppositories, at 2-week intervals. If no patient has a DLT observed by the cervix check after the last suppository, then the dose level will be considered safe.

With the dose escalation algorithm, there will be less than 9% probability to escalate to the next higher dose level if the DLT rate for the current dose level is 30%.

The maximum sample size for dose escalation is 39. Based on our experience in investigator-initiated therapeutic trials in this patient population at this institution, our anticipated accrual rate is 20-25 patients per year.

At the end of dose escalation phase, one dose will be selected for the expansion phase from dose levels II-IV that are considered safe. In general, the lowest dose level with significant within subject decreases in viral load (from baseline at Week 15) and lesion clearance to CIN1 or less will be selected (see Section 12.2 for details). If none of the safe doses achieve significance for decrease in viral load and lesion clearance, a decision will be made based on the totality of safety and efficacy profiles of the dose levels considered safe.

A cohort of 12 patients will be enrolled and treated at the selected dose level at the expansion phase to further evaluate the safety and efficacy of Artesunate.

